TES (as administered by the Nexalin apparatus) may be a viable alternative to ECT. A prior randomized, controlled trial compared antidepressant medication with Sham TES, Placebo with Nexalin at a lower dose, and Placebo medication with Nexalin at a higher dose. All three conditions showed remission of depressed mood by the end of treatment and maintenance of remission status following 12 weeks of follow-up. Thus, the effect sizes for Nexalin treatment were comparable to antidepressant medication. It should also be noted that the Nexalin device has undergone extensive safety analysis indicating that the device is safe for its intended use. Additionally, the classification of the device places it into a nonsignificant risk (low risk device) category. A review of Phase III Pivotal Clinical Trials (with a follow up period of one year) demonstrates that Nexalin TES Therapy does not result in any significant adverse events or side effects. In fact, there was no significant difference between reported events in the placebo group and reported events in the active treatment group.

[figure not shown]
Since the direct electrical stimulation represents a similar mechanism of action to ECT, and Nexalin has not only demonstrated effectiveness in depression but also has a much better safety profile than ECT, it is possible that Nexalin treatment could be a viable, more acceptable, alternative to ECT.

STUDY GOAL

Determine whether Nexalin TES is a viable alternative to ECT in subjects who do and do not accept ECT treatment.

STUDY DESIGN

A 2x2 factor Randomized Controlled Trial with block randomization. Inpatient subjects at the Carrier Clinic who are referred for ECT will be recruited, typed regarding their acceptance of ECT, and randomized to either treatment with TES or to a Sham condition. Treatment non-responders in either condition will continue as inpatients at the Carrier Clinic until they reach acceptable levels of functioning to be discharged. For additional details, see "procedures" section of this document.

STUDY DURATION

The study will last up to 2 years. This will allow sufficient time for recruitment and completion of all subjects.

TARGET POPULATION

Patients diagnosed with major depressive disorder (MDD) who have failed antidepressant therapy with one or more medications and are referred for ECT.

INCLUSION CRITERIA

To be included in the study, patients must be:

1. In-patients at the Carrier Clinic
2. Adults over age 18 and under age 65

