3. Able to speak, read and write fluently in English, assessed by the study coordinator at Carrier Clinic
4. Screened Negative for alcohol abuse and/or dependence
5. Able to provide informed consent, assessed by the study coordinator at Carrier Clinic
6. Referred for ECT
7. Not currently taking hypnotics or be prescribed hypnotics during the Nexalin trial.
8. Not pregnant or intending to become pregnant during the study
9. Committed to completion of the study.

TOTAL SUBJECTS ENROLLED

150

VULNERABLE POPULATIONS

No vulnerable populations (as defined by socio-economic status, geography, gender, age, disability status, and other populations identified to be at-risk for health disparities) will be recruited.

RECRUITMENT & RANDOMIZATION

As noted above, patients will be directly recruited from, and receive treatment at, the Carrier Clinic. Currently, the Carrier Clinic treats approximately 1,000 unique patients who receive ECT annually, resulting in 5,200 procedures performed per year. Randomization will occur in blocks, such that for every 20 subjects enrolled, 10 will receive Nexalin and 10 will receive Sham treatment.

COMPENSATION

No financial compensation will be provided to participants for participation in the trial.

PRIMARY OUTCOMES

Percent responders and non-responders to TES treatment or Sham TES treatment (who accepted or refused ECT) as assessed with the PHQ-9 (50% reduction or a score below 10).

SECONDARY OUTCOMES

Assess whether Nexalin TES produces significantly greater gains than Nexalin Sham for

1. Depression severity (as assessed with the PHQ-9, and the QIDS)
2. Anxiety severity (as assessed with the GAD-7 and the POMS)
3. Insomnia severity (as assessed with the ISI)

Finally, we will (post hoc) assess which baseline subject characteristics differentiate between responders and non-responders.

PROCEDURES

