All patients referred for ECT and otherwise eligible for the study will be approached by the Carrier Clinic study coordinator (or his designate) and asked whether they wish to participate in the research study. All subjects will be non-responders to traditional medical approaches (patients diagnosed with MDD who have failed antidepressant therapy with one or more medications). Those that express interest will review the study protocol with the study coordinator. The study coordinator will ascertain eligibility, address any concerns, and obtain written informed consent. Following the obtention of informed consent, the subject will be scheduled (or undergo at the time) a baseline assessment. The subjects that volunteer, are eligible, and are consented for the study will be queried as to whether or not they are willing to receive ECT. This decision will be used to type each subject that consents to be in the protocol (Accept or Refuse ECT). Following randomization to one of two conditions (TES or Sham), treatment will occur twice daily (40 minutes per session, separated by 5 hours' time between the AM and PM sessions) over 3-10 days. Subjects that do not exhibit 20% attenuation of symptoms (as assessed by an AM and PM version PHQ-9) on or before 6 treatments will be designated treatment non-responders and discontinue their participation in the study while remaining as inpatients at the Carrier Clinic. Note: During the Nexalin trial, all subjects will receive standard inpatient care where the only difference in the treatment regimens are that they are receiving TES or Sham TES in place of ECT. See "Protection Against Risks" section for stopping rules during treatment for subjects who do not show sufficient treatment response.

Session Protocol. The protocol for receiving treatment will be as follows:

1. Inpatients that have enrolled in the study will receive TES or Sham TES once in the AM and once in the PM.
2. The procedure will be conducted in a semi-private room while the subject reclines in a lounge chair.
3. The two TES session will each be 40 minutes in duration, separated by 5 hours' time.
4. The TES provider will oversee the administration of the patient on-line questionnaires.
5. The TES trained provider will complete the Carrier Clinic staffforms.
6. When the TES session is complete, the subject will resume his/her regular clinic activities.

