	7	PHQ-9	1 min	●	●			
	8	GAD-7	1 min	●		●		
	9	POMS	10 min	●		●		
	10	FACES	1 min		●			
Clinician	1	Patient Enrollment	2-5 min	●				
	2	Procedure Tracking	2-5 min		●			
	3	Adverse Event	5 min				●	
	4	Clinician Information	2-5 min	●				
	5	SBJ d/c Form	2-5 min					●

ASSESSMENT OF SUBJECT CLINICAL STATUS

As noted above, patient status will be assessed at baseline, twice daily (pre-post each session), once daily, and once every three days. The instruments will be administered on-site via an internet data portal (constructed with RedCap).

Subject Measures. All self-report instruments used in the study are listed below along with their administration schedule and a brief explanation regarding what the instrument measures.

1. **Demographics** (*completed once at baseline / intake*): All subjects will report age, sex, education level, **race/ethnicity**, and other relevant demographic and socioeconomic information.

2. AFQ * CAGE (completed once at baseline / intake): These instruments are standard alcoholism screening tools. Subjects who screen positive for alcoholism will not be included in the study.
3. Patient Expectancy (completed at baseline): Subjects will be asked to rate on a 0-5 Likert scale the degree to which they agree with the following statements: (1) This treatment will work, (2) This treatment will help my depression, (3) This treatment will help my anxiety, (4) This treatment will help my sleep, (5) This treatment will improve my quality of life.
4. QIDS (completed at baseline and once every three days): The 16 item Quick Inventory of Depressive Symptomatology (QIDS) is designed to assess the severity of depressive symptoms. The QIDS is a self-administered instrument that assesses all the criterion symptom domains designated by the DSM-IV. The patient is asked to rate the severity and frequency of specific symptoms present over the last 7 days. Each item is interval scaled from 0 to 3. It takes approximately 5 to 7 minutes to complete and the total score is obtained by adding the scores. The summary score ranges from 0 to 27. Threshold values are as follows: \leq 9 (Not Depressed); 10-13 Mild Depression; Moderate to Severe Depression 14-17; $>$ 18 Severe Depression.

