5. ISI (Completed at baseline and at the end of treatment): The Insomnia Severity Index is a brief insomnia screening tool that is the gold standard for quantifying severity of clinical insomnia symptoms. This will be administered at the beginning and end of treatment (e.g., 1st and 10th session).
6. SAFTEE (completed once every 3 days): The Systematic Assessment of Treatment-Emergent Effects was developed by the NIH to comprehensively catalog any physical symptoms experienced during psychiatric clinical trials along 16 subscales. This measure will be used to systematically measure symptoms and symptom categories.
7. PHQ-9 (completed in the AM and PM session): The Patient Health Questionnaire 9 is a brief, well-validated screening tool for depression. It has shown good reliability and validity for likely depression diagnosis and provides a means of assessing depression severity. The instrument in the present study has been modified so that it may be 1) administered twice daily and 2) used to track nightly sleep via 4 sleep related items
8. GAD7 (completed at baseline and once every 3 days): The Generalized Anxiety Disorder 7 questionnaire is a brief global screening measure of anxiety. It is well validated and is a standard screening tool for anxiety. This scale will allow for separate characterization of anxiety symptoms in addition to depression.
9. POMS (completed at baseline and once every 3 days): This is a 37-item adjective checklist where each item is rated on a 0-4 unipolar scale that ranges from not-at-all to extremely. The scored instrument provides values for six constructs including: tension-anxiety; depression-dejection; anger-hostility; fatigue-inertia; vigor-activity; and confusion-bewilderment. The outcome variables are measured in terms of the 6 factors and a total score, which are arrayed as T-Scores (standardized means of 50 +/-10).
10. “Faces” Mood Rating Scale (completed daily pre-post to each TES session): This is a single item 7 point bipolar rating scale for mood (from very happy to very sad). The measure is arrayed from -3 to +3.

Clinician Measures. All the clinician instruments to be used in the study are listed below along with their administration schedule and brief explanation regarding what the instrument measures

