1. Patient Enrollment Form / Candidate Screener / Enrollment Form (completed once per week per patient): This requires the staff member to profile the patient who has been approached to participate in the study and to document if they meet eligibility and have been consented.
2. Procedure Tracking form / Patient Tracking (once per session): This requires the clinician to record: the patient initials; the patient PNC ID; the date of the session; the session #; the time session was conducted; the room the session was conducted in; the identifying sticker attached to the device; the device number; whether each instrument was administered; any comments they may have about the session; whether the

patient was diagnosed with any new disorders (and if yes, please list); and whether the patient's meds have been changed (and if yes, please list).

3. Adverse Event Form (*completed as needed*): This requires the clinician to record: the patient initials; the patient PNC ID; the date of the session; description of event; information about the event onset; start date and start time of event; information about the event offset; end date and end time of event; actions taken or treatments given; the severity of the event; event symptoms; diagnostic results; information about outcomes; and if the event is on-going what additional steps are planned.

4. Clinician Information Form (*completed once*):

This requires the clinician to record: the study clinician identification number, the clinician's name, the clinician's position at the clinic, the clinician's credentials (degree), and the clinician's contact information.

5. SBJ d/c Form (*completed as needed*):

This requires that a staff member specify that a subject has been withdrawn from, or quit, the protocol and the reason for why the subject is no longer participating.

ANALYSIS PLAN

The primary analysis for the study will be an evaluation of treatment response rates using an analysis of 2x2 contingency tables, using the Cochran-Mantel-Haenszel test to assess differences in treatment response by randomization groups, stratified by patient choice. The secondary analysis will evaluate how treatment non-responders and responders differ with respect to the various demographic and clinical profile measures.

CONFIDENTIALITY

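### Optional efficiency gain, not a defect: the primary CMH test is valid but does not adjust for baseline PHQ-9; the likely return ranges from nothing to several points of power, depending on unstated inputs

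*Combined protocol and SAP*

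**What the plan says.** The ANALYSIS PLAN fixes the primary analysis as a comparison of response rates "using the Cochran-Mantel-Haenszel test to assess differences in treatment response by randomization groups, stratified by patient choice". The choice in question is whether the patient accepts or refuses ECT. The only other analysis named there contrasts responders with non-responders on demographic and clinical measures, which is not an adjusted treatment effect.

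PRIMARY OUTCOMES defines PHQ-9 response as "50% reduction or a score below 10". Under PROCEDURES, an earlier gate applies: "Subjects that do not exhibit 20% attenuation of symptoms (as assessed by an AM and PM version PHQ-9) on or before 6 treatments". The plan classes these patients as non-responders, and they leave the study at that point.

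Baseline PHQ-9 is available. ASSESSMENT OF SUBJECT CLINICAL STATUS says that "patient status will be assessed at baseline, twice daily (pre-post each session), once daily, and once every three days", and the schedule table marks PHQ-9 at baseline and at each session. TARGET POPULATION reads "Patients diagnosed with major depressive disorder (MDD) who have failed antidepressant therapy with one or more medications and are referred for ECT". Neither it nor INCLUSION CRITERIA sets a minimum PHQ-9 score.

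**The concern.** Adjusting a randomised comparison for a strong baseline predictor usually raises power without more patients. Baseline PHQ-9 is a natural candidate. It is already collected, and the response rule asks different falls of different patients: below 18 the under-10 criterion is the easier one, from 18 up the halving criterion governs. If follow-up scores track baseline closely, a patient's starting score says much about the chance of responding, and the planned test leaves that information unused. At stake is some power in the single primary test of a trial of 150 that states no power calculation. Type I error of the planned test is not in question.

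**Working it through.** **The plan's own figure.** TOTAL SUBJECTS ENROLLED gives 150, with no alpha, power or response rates, so it cannot be reproduced. For orientation, take 75 per arm, two-sided 5% and a 20-point difference (all but the 75 assumed):

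z = [d√n − 1.96√(2p̄(1−p̄))] / √(p₀(1−p₀) + p₁(1−p₁))

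- 20% v 40%: (1.732 − 1.270)/0.632 = 0.73, power 77%.
- 40% v 60%: (1.732 − 1.386)/0.693 = 0.50, power 69%.

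A few points of power would therefore be worth having.

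**Fall needed at the final outcome.** A responder must finish at or below half of baseline, or at 9 or less.

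| Baseline | Fall needed | Percent |
|---|---|---|
| 10 | 1 | 10 |
| 11 | 2 | 18 |
| 12 | 3 | 25 |
| 14 | 5 | 36 |
| 16 | 7 | 44 |
| 17 | 8 | 47 |
| 18 to 27 | 9 to 14 | 50 to 53 |

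The 20% gate is a separate hurdle at or before treatment 6: 2 points from 10 and 3 points from 11. It need not hold at the end. A patient starting at 11 can pass the gate with a 3-point fall, finish at 9, and respond.

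**Simulation, main model.** From the documents: 150 patients, 1:1 allocation, the response rule and the six-treatment rule. Assumed:

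- two-sided 5%; effect 2.5 points; mean improvement without TES 7 points; residual SD 5;
- PHQ-9 scored 0 to 27 (the plan says "The instrument in the present study has been modified so that it may be 1) administered twice daily"); baseline rounded normal, redrawn outside 10 to 27;
- half accept ECT, with no effect of that choice on outcome;
- the score after treatment 6 carries 60% of the expected change, with residual SD 4 and correlation 0.6 with the final residual; a fall under 20% means leaving as a non-responder.

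In this model 27–35% leave with TES and 40–50% with Sham. Power (%) of the logistic likelihood-ratio test without → with baseline, 10,000 replicates, by slope of follow-up on baseline:

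| Baseline mean, SD | 1.0 | 0.7 | 0.5 | 0.3 |
|---|---|---|---|---|
| 17, 5 | 55.0→60.3 | 61.5→62.8 | 64.9→64.9 | 64.7→64.5 |
| 19, 4 | 57.3→60.9 | 62.5→63.5 | 63.3→63.2 | 64.8→64.7 |
| 21, 3.5 | 57.6→60.0 | 61.7→62.4 | 62.1→61.8 | 62.3→62.5 |

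The gains are 2.4 to 5.3 points at slope 1.0, 0.7 to 1.3 at 0.7, and −0.3 to +0.2 at 0.5 or less. The CMH test lies 0.6 to 1.4 points below the unadjusted logistic test; that difference is not counted as gain. At slope 1.0 the variance ratio is 1.06 to 1.16, equivalent to 150 × 1.06 = 159 up to 150 × 1.16 = 174 patients.

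**Slope as correlation.** r = bσ/√(b²σ² + 25), where σ is the baseline SD after redrawing. SD 5 becomes about 4.12 and SD 3.5 about 3.24.

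- Slope 1.0: 4.12/√(17.0 + 25) = 0.64; 3.24/√(10.5 + 25) = 0.54.
- Slope 0.7: 2.88/√(8.3 + 25) = 0.50; 2.27/√(5.1 + 25) = 0.41.

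**Sensitivity.** Gain in points at slope 1.0 / 0.7 / 0.5 or less:

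- baseline floor 5: 3.0–5.8 / 0.6–1.7 / −0.3 to 0.2;
- gate met if any of six scores shows a 20% fall: 2.8–7.5 / 0.9–2.4 / −0.5 to 0.4;
- effect 3.5 points: 2.4–5.0 / 0.3–1.1 / −0.2 to 0.1.

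**Second set of models.** These used baseline means 16 to 20, SD 4 or 5, and effects set for CMH power of about 68–79%. Gain is the adjusted score test minus CMH, under the six-treatment rule:

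| Correlation | Gain, points |
|---|---|
| 0.2 | 0.8 to 1.7 |
| 0.4 | 0.1 to 0.8 |
| 0.5 | 0.5 to 1.9 |
| 0.6 | 1.0 to 3.8 |
| 0.65 | 2.8 to 4.6 |
| 0.7 | 3.3 to 6.7 |
| 0.8 | 8.5 to 13.9 |

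Varying follow-up SD, mean and timing gave up to 2.5 points at 0.5 and 4.2 to 8.8 at 0.7. A model with percentage reduction independent of baseline (correlation 0.43 to 0.77) gave 0.1 to 4.6.

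**Type I error under the rule, main model.** CMH 4.5–5.5%, logistic 4.9–5.9%, standardised risk difference 4.8–5.8% (Monte Carlo SE 0.2).

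**The case against.** The CMH test is standard for a binary endpoint, is stratified by the design's own second factor, and holds its type I error. The endpoint already uses baseline through the 50% criterion. In the main model only 3 of 12 cells gain more than 2 points, all at slope 1.0, where point improvement is unrelated to starting severity; nothing in the documents supports that slope. Patients referred for ECT may mostly start at 18 or above, where the percentage fall needed is flat and there is less to gain. The six-treatment rule reduces the gain further, because leavers are non-responders whatever their later course. All of this stands, and it makes the change optional.

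It does not remove the point. Halving relative to baseline does not take out the dependence on baseline created by the under-10 criterion, and the correlation needed for a useful gain, roughly 0.55 to 0.7, is not extreme.

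A reader might infer three stronger things that the documents do not support. One is that the planned test is invalid or biased; it is neither. Another is that adjustment would reliably add power; the inputs that decide this are not stated. A third is that the same reasoning calls for a baseline-adjusted ANCOVA of PHQ-9 severity, a SECONDARY OUTCOMES item with no stated method. Patients who fail the six-treatment rule discontinue, and in the main model they do so at different rates by arm, so an ANCOVA of completers could be biased.

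**Conclusion.** The point holds as a cheap, optional improvement. With leavers counted as non-responders, adjusting for baseline PHQ-9 changes power by about −0.5 to +2.5 points if the baseline/follow-up correlation is about 0.5 or less. It adds about 2 to 7 points at about 0.55 to 0.7, although some scenarios near 0.6 gain only about 1. Seven points is not a ceiling: one scenario at 0.7 reached 8.8, and 0.8 gave 8.5 to 13.9. Everything beyond the sample size, allocation and the two PHQ-9 rules is assumed, so these are conditional ranges and not forecasts for this trial.

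**What to change.** Before unblinding, pre-specify the primary comparison as a logistic regression of response on arm, ECT choice and continuous baseline PHQ-9. Count patients who leave under the six-treatment rule as non-responders. Report a standardised risk difference with its confidence interval, and keep the CMH test by ECT choice as a sensitivity analysis. State the functional form of the covariate in the plan.

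The cost is analysis wording only; no new data or patients are needed. There are three downsides:

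- the marginal risk difference must be named as the estimand, because the logistic coefficient is a conditional odds ratio;
- the gain may be nil, or a loss of up to about 0.5 point of power;
- the likelihood-ratio or sandwich test can run slightly above nominal, up to about 5.9%. This comes from leaving CMH for a logistic test and not from the baseline term.

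Keeping the CMH test as primary would also be defensible.

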Transcranial electric stimulation devices are classified as a Class III device. These types of devices have been used for many years and occasional adverse effects have been reported, including: headache, nausea, minor burns, increased agitation, minor rash from specific electrodes, and electrical discharge when electrodes are removed. Specifically, headaches and nausea have been noted when current levels are higher than those used in the present study. Note: the device settings for current and duration of treatment are fixed (i.e., cannot be altered by the administering clinician or technician).

Risks associated with Sham treatment:

Since the sham treatment is identical except for a lack of active electrical current, the only risks include those associated with nervousness about the procedure and skin irritation from electrodes, described above.

Risks associated with questionnaires, interviews, and physical measurements:

As the subjects in the study are psychiatric patients with relatively significant symptoms, and the assessment measures directly address some of these symptoms, it is possible that answering questions in an interview format or in a questionnaire format can arouse uncomfortable feelings or even some level of distress. Although this is very rare, it is possible.

Risks associated with loss of confidentiality:

There is a possibility that records associated with the study (particularly paper documents such as those in the study binder) will inadvertently be seen by Carrier Clinic personnel that are not affiliated with the study.

Risks associated with ECT

While there are risks associated with ECT treatment, the provision of this therapy occurs outside the proposed protocol and therefore is not a risk of the proposed study.

PROTECTION AGAINST RISKS

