Study files that exist regulatory issues will be kept in a locked file cabinet behind a locked door at the office of the PI at Penn. Study files for active subjects will be kept in a separate, locked file cabinet in a locked room at the Carrier Clinic. Only those affiliated with the study will have access to these records.

POTENTIAL STUDY BENEFITS

It is possible that the Nexalin treatment (for those randomized to this condition) will ameliorate clinical symptoms.

RISK/BENEFIT ASSESSMENT

Greater than minimal risk. However, it should be noted that the current studies deviate from normal care by introducing a relatively low-risk procedure that may obviate the need for a more high-risk procedure. Thus, the potential benefits to the individual, as well as the information gained, outweigh the risks.

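### The goal and risk-benefit text concern an alternative that may spare ECT, but the plan has no ECT-receipt outcome and schedules no assessment after the last session

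*Combined protocol and SAP*

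**What the plan says.** - **Purpose.** The STUDY GOAL reads: "Determine whether Nexalin TES is a viable alternative to ECT in subjects who do and do not accept ECT treatment". All patients have been referred for ECT (INCLUSION CRITERIA). The RISK/BENEFIT ASSESSMENT rates the trial above minimal risk and describes the intervention as "a relatively low-risk procedure that may obviate the need for a more high-risk procedure".
- **Outcomes.** The primary outcome is PHQ-9 response: a halving of the score, or a score under 10. Secondary outcomes are depression, anxiety and insomnia scales. The ANALYSIS PLAN compares response between arms, stratified by ECT acceptance, and then compares responders with non-responders.
- **Treatment period.** Under PROCEDURES, "treatment will occur twice daily (40 minutes per session, separated by 5 hours' time between the AM and PM sessions) over 3-10 days", on weekdays only, for 6 to 20 sessions.
- **Assessment period.** The schedule covers baseline and the treatment period. The latest point named is the ISI at the end of treatment. Under CONFIDENTIALITY, the portals accept data session by session only.
- **Early leavers.** Patients without a 20% fall in PHQ-9 by six treatments "discontinue their participation in the study while remaining as inpatients at the Carrier Clinic".
- **ECT.** During the trial, TES or sham replaces ECT. Under POTENTIAL STUDY RISKS, "the provision of this therapy occurs outside the proposed protocol and therefore is not a risk of the proposed study".
- **Exit form.** The SBJ d/c Form is described thus: "This requires that a staff member specify that a subject has been withdrawn from, or quit, the protocol", together with the reason.

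**The concern.** The question is whether these patients, already referred for ECT, can be spared it. Because TES or sham is given instead of ECT, any ECT comes after study treatment stops, and that is where scheduled observation stops too. The advantages claimed in BACKGROUND (no seizures, no sedation, lower expense) follow only if ECT is in fact not given.

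Whether a patient went on to have ECT can be compared between the randomised arms, and sham is an adequate control for it. The point is therefore separate from the absence of an ECT comparator. If ECT receipt is not collected, no later analysis of study data can supply it, and the trial's own headline question goes unanswered even if the PHQ-9 result is clearly positive.

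**Working it through.** **1. Length of observation.** The plan's own figure reproduces. At two sessions a day, 6/2 = 3 and 20/2 = 10, which matches the stated 3-10 days. With Monday-to-Friday treatment, the calendar span counted inclusively is:

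| Treatment days | Start day | Calendar days |
|---|---|---|
| 3 | Monday to Wednesday | 3 |
| 3 | Thursday or Friday | 5 |
| 10 | Monday | 12 |
| 10 | Tuesday to Friday | 14 |

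Scheduled assessment after the last session: 0 days. No sentence says this. It is inferred from the assessment table, the descriptions of the instruments and the per-session data entry, and nothing in the documents contradicts it.

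**2. Search for ECT data.** There are 15 instruments, 10 for patients and 5 for clinicians.
- None of the patient questionnaires is described as covering ECT use.
- The procedure tracking form covers new diagnoses and medication changes at each session.
- The exit form covers patients who withdrew or quit, and why, so a patient who completes treatment would not obviously have one.
- Willingness to have ECT is asked once, after consent and before randomisation. It defines the stratum and is not an outcome.

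**3. Purpose against measurement.**

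| Claim | Data needed | Data planned |
|---|---|---|
| TES reduces symptoms more than sham in the short term | PHQ-9 during treatment, by arm | Yes |
| TES spares patients ECT | ECT receipt after study treatment, by arm | No |
| Response lasts | Assessment at a fixed later time | No |

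**4. What an ECT-receipt outcome could show.** The documents give no ECT-use rate, no share of acceptors, and no alpha or power for the 150. The following is therefore an illustration. Assumptions: two-sided alpha 0.05, 1:1 allocation, no dropout, and ECT use in the sham arm of 40%, 50%, 60% or 80%. With n per arm and p̄ the mean of the two rates,

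power = Φ{ [Δ − 1.96·√(2p̄(1−p̄)/n)] / √[(p1(1−p1)+p2(1−p2))/n] }.

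*Acceptors only, half of patients assumed to accept:* 150/2 = 75, about 37 per arm. For 60% against 40%: [0.20 − 1.96·√(0.50/37)] / √(0.48/37) = (0.200 − 0.228)/0.114 = −0.24, so power is 40%. Over the four sham rates, power is 40-47% for a 20-point drop and 75-86% for a 30-point drop.

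*All 150, 75 per arm:* 69-77% for a 20-point drop and 87-94% for a 25-point drop. These figures flatter the design. If refusers have ECT in neither arm and half of patients accept, a 20-point drop overall needs 0.20/0.5 = 40 points among acceptors.

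**The case against.** Much of the case on the other side stands, and it limits what can be claimed.

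- **The ECT sentence is about risk.** It says that ECT harms are not study harms. A reader might infer that it bars ECT data, but it does not. The gap shows in the outcomes and the schedule.
- **The claims are hedged.** The risk-benefit text says only that TES may spare ECT and also cites the low risk of the procedure and the information gained. The stated benefit is symptom relief, which the PHQ-9 does measure. So the justification does not rest on ECT avoidance alone. The STUDY GOAL, however, names ECT directly.
- **The prior trial.** BACKGROUND reports 12 weeks of maintained remission, but the conclusion it draws is that effects were comparable to antidepressants. It is not cited to prove durability.
- **The forms are not reproduced.** The reason field on the exit form could capture leaving for ECT, and ECT would appear in clinic charts. The fair statement is that no ECT outcome is specified.
- **ECT receipt is not a clean endpoint.** It reflects patient and clinician choice. It is also partly downstream of self-report, because the PHQ-9 rule decides who leaves study treatment by session 6.

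Three stronger readings are tempting but unsupported:

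1. *That observation ends before any ECT decision.* Acceptance or refusal is recorded before randomisation. What goes unobserved is ECT decided on or received after treatment.
2. *That a patient who responds on the last day, relapses and then has ECT is scored a success.* PRIMARY OUTCOMES gives no time point, so last-day scoring is an assumption.
3. *That early leavers go before the typical one-week ECT wait has passed.* The documents do not say when that wait starts.

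**Conclusion.** The point holds as a gap between the stated goal and what is measured. As planned, the trial can support a short-term PHQ-9 difference between TES and sham. It cannot support a claim that TES spared patients ECT or that response lasted. A reader might infer that the primary analysis is therefore invalid. It is not on this ground, since the randomised sham comparison of PHQ-9 response does not depend on later ECT.

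The gap affects all 150 patients: none has a scheduled assessment after the last session, and those stopped by session 6 are followed for three treatment days at most. The absence of follow-up is inferred from the schedule. The power figures rest on an assumed acceptor share and assumed ECT-use rates. They are reason to make ECT receipt a secondary outcome, not to omit it.

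**What to change.** 1. **Collect the data.** Extend the SBJ d/c Form with three chart-based fields: ECT given (yes/no), date of first ECT, and discharge date. Complete it for every randomised patient, including those who finish treatment and those who stop by session 6.
2. **Keep patients in data collection.** Amend PROCEDURES so that patients who stop study treatment remain in this record. This changes neither the stopping rule nor any decision about ECT.
3. **Add a secondary outcome.** ECT received within one pre-specified window counted from randomisation, TES against sham, by assigned arm. Take the ECT-accept stratum as the main reading and show all randomised patients alongside. As a guide to length, the longest course plus the typical wait is 14 + 7 = 21 days if the wait runs from the end of treatment, which is an assumption.
4. **Measure durability properly, if it is to be claimed.** Repeat the PHQ-9 at a fixed time after randomisation and count patients who have had ECT as not maintaining response to study treatment. A PHQ-9 at discharge would not serve: discharge depends on improvement, its timing varies, and it may follow ECT.
5. **Otherwise narrow the claims.** If these data are not collected, reword the STUDY GOAL and the RISK/BENEFIT ASSESSMENT to short-term response against sham.

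**Cost.** Three fields on an existing form, chart look-up at a clinic that itself gives ECT and already supplies medical record numbers, and a consent sentence if the present text does not cover it. The optional PHQ-9 takes one minute but needs contact with patients who may have been discharged. ECT given elsewhere would be missed, and the comparison among acceptors would have low power.
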